6. Able to use Facebook
7. Able to use Skype, FaceTime or Zoom
Exclusion
Pregnancy complications that require emergency care
2. Thyroid disease
3. Multiple gestation
4. Substance abuse within last 3 years
5. ART (Assisted Reproductive Technology) pregnancy
6. Current smoker
7. Prior bariatric surgery
8. In weight-loss program within 3 months of conception
9. BMI ≥ 35
10. Unable to attend intervention/follow-up visits
11. Unwilling to self-monitor data collection
12. Unable to complete intervention
13. Presence of any condition that limits walking
14. Presence of any condition that limits following diet
recommendations
15. Pregnancies complicated with fetuses diagnosed with
lethal malformations/conditions

If the participant meets enrollment criteria, then the research coordinator will call her again to assign her a time and place for the orientation session, to complete study-related survey instruments, and to obtain her email address to provide her with informed consent materials for review. Participants are informed that they will earn incentives to continue and complete the study: (1) a \$50 gift card at study entry, (2) a digital scale and pedometer at delivery, and (3) a gift up to \$75 for baby at Walmart's baby registry at study closure. Investigators will issue incentives in accordance with policies set forth by

IRB (please refer to the heading titled "Self-Administered Surveys and Incentive to Participate" below for additional detail regarding participant incentives).

Our recruitment target of overweight or obese pregnant women will involve 50% Hispanic women (who are English-speaking) and 50% other race including non-Hispanic whites. We anticipate meeting our recruitment goals through multiple approaches. We will promote the study via targeted mailings and clinic posters. We will advertise and develop study materials in English only. We will recruit over a period of 9 months, planning to randomize 2-3 participants

each week, or 1-2 participants per site. Our goal is to randomize a total of 72 pregnant women (24 women in each study arm, 12 women per site). Given an attrition rate of 20%, this will leave us with 60 women total (20 women in each study arm, or 10 women per site in each study arm).

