Sample Size and Randomization. The primary outcomes of interest are: (1) postpartum weight loss; (2) HbA1c and mean arterial blood pressure; and (3) breastfeeding duration. A total of 60 participants (20 per study arm) will be recruited. The results from this pilot study will be used in sample size estimation for a future study that is sufficiently powered to detect a clinically meaningful effect size. Due to the nature of this project being a feasibility study, the sample size in the proposed study is not based on providing adequate power to detect a clinically meaningful effect size across the three study arms. Block randomization with block size of 5 participants will be employed. A sequence of 12 random integers will be generated using a computer algorithm. The first 4 integers of the sequence will be assigned to the DPP plus breastfeeding arm; the next 4 integers will be assigned to the DPP only arm; and the last 4 will be assigned to the usual care arm. Blocks will be assigned to arms in the increasing order of sequence of integers generated.

**Statistical Analysis.** For baseline data characteristics, descriptive statistics will be reported as mean and standard deviation for continuous variables and as count and percentage for categorical variables. Depending on the distribution of the continuous variables, the Kruskal-Wallis test or ANOVA will be used to test for differences in continuous variables across the three arms. Chi-

Square test of independence (or Fishers exact test if 25% of cells have counts less than 5) will be used to assess the association between categorical variables and the three arms. The analysis will be based on "intention-to-treat" principle. A two-sided alpha level of 0.05 will be used to determine statistical significance. A 95% confidence interval will also be reported.

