Aim 1: Test the efficacy of Tx1 to improve 6-month postpartum weight loss among women with a BMI  $\geq$  25. The outcome of interest is 6 month postpartum weight loss measured across the three arms. Weight will be measured at delivery, and at weeks 1, 3, and 6 postpartum and at 3 months (13 weeks) and 6 months (26 weeks) postpartum. The difference in postpartum weight (weight loss) between two consecutive time points will be computed. Thus, each participant has 5 postpartum weight loss values based on weight measurements at 6 different time points. We will use the generalized estimating equation approach to compare weight loss in the DPP plus breastfeeding arm (Tx1) with weight loss in the DPP only (Tx2) and usual care (Tx3) arms, as well as weight loss between Tx2 and Tx3. The working correlation matrix will be specified after assessing the data. The model will be adjusted for the effect of age, race/ethnicity, level of education, annual household income, family history of diabetes, baseline weight, pre-diabetes status, and parity.

Aim 2: Test the efficacy of Tx1 to improve 6-month postpartum mean blood glucose (HbA1c) and mean arterial blood pressure among women with a BMI  $\geq$  25. The outcome of interest is mean blood glucose (HbA1c) and mean arterial blood pressure ((systolic blood pressure +2 (diastolic blood pressure)/3)) measured at baseline, delivery, and at 6 months postpartum across the three arms. We will use a multiple linear regression approach to compare HbA1c in Tx1 with HbA1c in Tx2 and Tx3, as well as HbA1c between Tx2 and Tx3. The model will be adjusted for the effect of age, race/ethnicity, level of education, annual household income, family history of diabetes, pre-diabetes status, parity, and baseline weight. The difference in mean blood arterial pressure at 6 months postpartum will also be assessed using a separate multiple linear regression approach after adjusting for the same covariates listed previously.

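### The Aim 1 GEE names no small-sample variance or reference distribution; with the customary uncorrected sandwich, a single arm contrast would have about 7–12% two-sided error rather than the stated 5%.

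*Combined protocol and SAP*

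**What the plan says.** All of this is in Section III, Statistical Methods and Data Analysis, unless noted.

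- **Method (Aim 1):** "We will use the generalized estimating equation approach to compare weight loss in the DPP plus breastfeeding arm (Tx1" and the DPP-only and usual-care arms, plus the contrast between those two.
- **Outcome:** "each participant has 5 postpartum weight loss values based on weight measurements at 6 different time points".
- **Covariates:** the model is "adjusted for the effect of age, race/ethnicity, level of education, annual household income, family history of diabetes, baseline weight, pre-diabetes status, and parity".
- **Working correlation:** "The working correlation matrix will be specified after assessing the data". No candidate structures and no selection criterion are listed.
- **Error level:** "A two-sided alpha level of 0.05 will be used to determine statistical significance", and 95% confidence intervals are to be reported.
- **Number of women:** the statistical section says "A total of 60 participants (20 per study arm) will be recruited". Section II.D says "Our goal is to randomize a total of 72 pregnant women" and then "Given an attrition rate of 20%, this will leave us with 60 women total".

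The plan does not say which standard error the GEE will use (empirical or model-based), whether it is corrected for a small number of clusters, or whether test statistics are referred to a normal or a t distribution.

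**The concern.** GEE inference is justified as the number of independent clusters grows. Here the clusters are women, not the five weight differences each contributes, so 60 women supply 60 independent units and not 300. With two arm terms, an intercept and eight covariates, there are only about three to seven women per parameter.

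At that ratio the ordinary sandwich variance is biased downward, because the fitted model absorbs part of each woman's residual. The normal reference also ignores the uncertainty in the variance estimate. Both effects make p-values too small and intervals too short.

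Weight loss is the first of the listed primary outcomes, and Aim 1 is worded as a test of efficacy. The results are also meant to feed the sample-size calculation for a later trial, so understated uncertainty would carry forward.

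**Working it through.** **Inputs from the plan.** Two-sided level 0.05; three equal arms; five weight changes per woman; eight covariates; 60 or 72 women.

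**Number of women.** The plan's attrition arithmetic does not reproduce its 60: 72 × 0.8 = 57.6. The check therefore uses 57, 60 and 72.

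**Number of parameters p.** Intercept 1 + arm terms 2 + eight covariates at one term each = 11. If race/ethnicity and parity have three levels, and education and income four (assumed, since the plan gives no levels), the covariates take 4 + 2 + 2 + 3 + 3 = 14 terms and p = 17.

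**Other assumptions.** Uncorrected sandwich variance with a normal reference; no true arm effect; covariates unrelated to the outcome; several within-woman correlation patterns, since the plan gives none.

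**Step 1: size of the bias by hand.** Arm and all covariates are constant within woman, so with equal numbers of values per woman the independence GEE is a regression on each woman's mean change. Average leverage is p/n, and the sandwich standard error is roughly √(1 − p/n) of the true one. The nominal 1.96 then acts as 1.96 × √(1 − p/n):

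- n = 60, p = 11: √(1 − 11/60) = 0.904; cut-off 1.77; two-sided normal tail 7.6%.
- n = 60, p = 17: √(1 − 17/60) = 0.847; cut-off 1.66; tail 9.7%.
- n = 72, p = 11: √(1 − 11/72) = 0.920; cut-off 1.80; tail 7.1%.

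This leaves out the variability of the standard error itself, so the actual error should be somewhat higher.

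**Step 2: simulation of the GEE under no effect.** Test of Tx1 against Tx3, with 3,000 to 6,000 trials per setting (Monte Carlo standard error about 0.4 to 0.5 points). On a test dataset the code matched a standard package for the estimate and both standard errors. Uncorrected sandwich, normal reference, fixed simple working correlation:

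| Women | Error, p = 11 to 17 |
|---|---|
| 57 | 9.0–12.0% |
| 60 | 8.3–10.2% (p = 11); 10.7–11.5% (p = 17) |
| 72 | 7.2–10.2% |

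A simpler simulation on woman means agrees: 8.1% (p = 11) to 11.2% (p = 17) at 60 women, 9.0–11.8% at 57 and 8.0–9.8% at 72. Adding terms for the measurement interval (p = 15 and 20) gives 7.5–12.6%. Since interval coverage is one minus this error, an error of 7–12% means nominal 95% intervals covering about 88–93%.

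**Step 3: the data-driven working correlation.** Independence and exchangeable give the same arm test here, for the reason in Step 1. Selecting among independence, exchangeable and AR(1) by an information criterion (CIC) adds at most about 0.4 points. Unstructured is different. At 60 women, under one simulated weight-path pattern, the error goes from 10.0% to 12.4% (p = 11) and from 11.4% to 15.2% (p = 17). Across settings the addition is about 1 to 4 points.

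**Step 4: model-based standard error.** Rejection ran from 0.5% to 21%, depending on whether the working correlation was right.

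**Step 5: corrected inference at 60 women, p = 11 to 17.**

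- Kauermann-Carroll-type variance with t on n − p degrees of freedom: 5.2–6.1%.
- Scaling by n/(n − p) with t: 4.5–6.1% with a simple working correlation.
- Mancl-DeRouen variance with t: 2.1–3.8%, which is conservative.

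**The case against.** The strongest reply is that the plan never says it will use the uncorrected sandwich. A reader might infer that the planned analysis is known to reject about twice as often as it should. The documents do not support that: they leave the variance estimator open, and an analyst could choose a corrected one. What stands is that nothing in the plan requires this. The customary empirical choice misses the 5% level, and the model-based alternative is not safe either.

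A reader might also blame the working correlation chosen after seeing the data. Step 3 does not bear that out. Nearly all the excess comes from the uncorrected variance with few women per parameter, and the late choice matters materially only if unstructured is a candidate, on which the plan is silent.

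Third, 72 women may be analysed, given intention-to-treat and the planned imputation. That reduces the excess without removing it; at 72 women with 11 parameters, some runs fall to 7.2%.

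Last, this is a declared pilot, not sized for power, and no confirmatory decision rests on this test. That limits the consequences. But the plan disclaims power only; it keeps the 0.05 level and the 95% intervals.

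**Conclusion.** The point holds as a conditional one. With 57 to 72 women and 11 to about 17 parameters, the uncorrected sandwich with a normal reference would give a single contrast an error of about 7–12% with a simple working correlation (about 8–11.5% at 60 women), and intervals that are too short. This rests on two assumptions the plan does not settle: the variance estimator and reference distribution, and the covariate coding behind 17 parameters. The count of 11 needs only one term per covariate.

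It does not show that the trial will report inflated results. For a pilot, the main harm is over-read efficacy p-values and understated uncertainty passed to the next trial. The change should be made, because a stated error level should be matched by a method that delivers it.

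**What to change.** Add to the Aim 1 analysis in Section III that inference will use a small-sample-corrected sandwich variance of Kauermann-Carroll type, with a t reference on women minus parameters degrees of freedom. In place of the deferred choice, name a simple working correlation now, for example exchangeable. If a linear mixed model replaces the GEE, specify Kenward-Roger inference. State the coding of the categorical covariates, so that the parameter count is known before analysis.

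The cost is one or two SAP sentences and a software option; design, data collection and conduct are untouched. Intervals widen to their correct width. By the Step 1 approximation at 60 women, the ratio of half-widths is 2.01 / 1.77 = 1.14 with 11 parameters (t on 49 degrees of freedom) and 2.02 / 1.66 = 1.22 with 17 (t on 43), so about 14% to 22% wider.

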Aim 3: Test the efficacy of Tx1 to increase any breastfeeding through 6 months postpartum among women with a BMI  $\geq$  25. Hypothesis 3: Women in Tx1 will breastfeed longer compared to women in Tx2 and Tx3. At delivery, breastfeeding initiation will be measured (see Table 5). This is defined as starting breastfeeding immediately after delivery. We

will also measure the duration of any breastfeeding (defined as predominant breast milk with some formula supplementation) as outlined in Table 5 below. Further, we will measure exclusivity of breastfeeding (defined as exclusive breast milk without supplementation unless medically necessary), formula supplementation, and solid foods. We will measure formula and solid food at the time that they were first introduced as well as quantity and frequency of feedings.

Table 5. Timeline: Data Collection for All Study Participants

	Prenatal			Postnatal							
Measurements	Baseline	Week 24	Week 28	Week 32	Week 36	Delivery	1 Week	3 Weeks	6 Weeks	3 Months	6 Months
Breastfeeding Knowledge, demographics, health status	Χ										Χ
Breastfeeding Self-Efficacy Scale-Short Form (BSES-SF)	Х										Χ
Kaiser Physical Activity Survey (KPAS)	X										Χ
Fruit & Vegetable Intake Screener (EATS)	X										Χ
Selected items from DSQ (NHANES 2009-10)	Х										Χ
Mother's Weight (lbs)	Х					Х	Χ	Χ	Χ	Χ	Χ
Mother's Height (inches)	Х										
Glucose tolerance	Х										
Mother's HbA1c	Х										Χ
Mother's Mean Arterial Blood Pressure	Х					Χ					Χ
Baby's Weight (kg)						Х	Х	Х	Х	Х	Χ
Baby's Height (gm)						Х	Х	Х	Х	Х	Χ
Breastfeeding Initiation at Delivery						Χ					
Breastfeeding Duration (any and exclusive)							Χ	Х	Х	Х	Χ
Formula Supplementation						Х	Χ	Χ	Χ	Χ	Χ
Solid Foods							Х	Х	Х	Х	Χ

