Comparison of scores on the Breastfeeding Assessment, BSES-SF, KPAS, EATS, and selected items from the DSQ. The Breastfeeding Assessment is based on 44 questions. Cronbach's alpha will be used to test the internal consistency of the data. The "difference in Breastfeeding Assessment scores between recruitment and at study closure" across all three study arms will be assessed using the multiple linear regression approach. The model will be adjusted for the effect of age, race/ethnicity, level of education, annual household income, family history of diabetes, pre-diabetes status, and parity. The BSES-SF score is based on 14 questions and ranges from 14 to 70 points. Cronbach's alpha will be used to test the internal consistency of the data. The "difference in BSES scores between recruitment and at study closure" across all three study arms will be assessed using the multiple linear regression approach. The model will be adjusted for the effect of age, race/ethnicity, level of education, annual household income, family history of diabetes, pre-diabetes status, and parity. The KPAS score comprises of 38 questions that are distributed sequentially but non-uniformly across four sections and measure household and family care activities (household index); occupational activities (occupational index); active living habits (active living index); and participation in sports and exercise (sports and exercise index). For each section, Cronbach's alpha will be used to test the internal consistency of the data. For each index of physical activity, "difference/change between recruitment and at study closure" across all three study arms will be assessed using the multiple linear regression approach after adjusting for the effect of the previously stated covariates. The EATS survey consists of 10 questions, and up to 6 questions will be selected from the DSQ. For each question, counts and percentages will be reported for participants at recruitment and at study closure across all three study arms.

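### The Aim 2 models for HbA1c and mean arterial pressure, both primary outcomes, leave out the baseline value of the outcome, which is already collected; this gives up some precision

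*Combined protocol and SAP*

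**What the plan says.** Section III, Sample Size and Randomization, gives the primary outcomes: "The primary outcomes of interest are: (1) postpartum weight loss; (2) HbA1c and mean arterial blood pressure; and (3) breastfeeding duration".

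Under Statistical Analysis, Aim 2, the HbA1c analysis reads "We will use a multiple linear regression approach to compare HbA1c in Tx1 with HbA1c in Tx2 and Tx3". The covariates are age, race/ethnicity, education and household income, followed by "family history of diabetes, pre-diabetes status, parity, and baseline weight". That makes eight. For blood pressure the plan says "The difference in mean blood arterial pressure at 6 months postpartum will also be assessed using a separate multiple linear regression approach", with the same eight covariates.

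In Table 5 the row "Mother's HbA1c" is marked at baseline and 6 months. The row "Mother's Mean Arterial Blood Pressure" is marked at baseline, delivery and 6 months. So the baseline of each outcome will be in the database, but neither is on the covariate list and no other section puts it there.

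The survey comparisons at the end of Section III model change from recruitment to closure, for example "difference in BSES scores between recruitment and at study closure". The adjustment list there ends with "family history of diabetes, pre-diabetes status, and parity": seven covariates, again without the baseline score. This covers six models (Breastfeeding Assessment, BSES-SF and the four KPAS indices).

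**The concern.** The baseline measurement of a continuous outcome is often the best single predictor of its later value. The MAP model spends degrees of freedom on income, education and parity but contains no blood pressure covariate. Pre-diabetes status, which the documents do not define, may partly stand in for baseline HbA1c; nothing on the list does that for MAP. The Aim 1 weight model, by contrast, does include baseline weight.

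Precision is at stake, not validity. Section III promises 95% confidence intervals and says the pilot results will feed the sample size of a later trial. Leaving out the baseline value widens those intervals. It also leaves chance imbalance in the outcome uncorrected: with 20 per arm and individual allocation, some pair of arms will differ by more than 0.5 SD on a given baseline measure in about 25% of trials.

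The no-bias statement assumes that women are allocated individually. The block text in Sample Size and Randomization can be read as sending whole blocks of 5 to one arm. That is a separate issue, which baseline adjustment would not cure.

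**Working it through.** The plan states no SD, effect size, power or baseline-to-6-month correlation for either outcome, so there is no figure of its own to reproduce.

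**Inputs from the documents.** N = 60 completers (Section II.D), three arms, two-sided 5% level, and q = 8 covariate columns if each covariate takes one column. I also used q = 14 as an assumption to allow for dummy coding.

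**Assumption.** r is the partial correlation of the baseline value with the 6-month value, given the listed covariates.

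**Formula.** Error degrees of freedom without baseline: f = 60 − 3 − q = 57 − q. The ratio of 95% interval widths, with baseline to without, is

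sqrt(V × (1 + 1/(f − 2))) × t(f − 1)/t(f)

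V is the residual variance ratio. The term 1/(f − 2) is the average penalty for chance imbalance in the added covariate, and t is the 97.5% point.

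**6-month value, V = 1 − r².** With q = 8, f = 49, t(49) = 2.0096 and t(48) = 2.0106. At r = 0.4: sqrt(0.84 × (1 + 1/47)) × 2.0106/2.0096 = 0.927, so the interval narrows by 7.3%. In the table a negative figure means widening.

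| r | q = 8 | q = 14 |
|---|---|---|
| 0 | −1.1% | −1.3% |
| 0.2 | 0.9% | 0.8% |
| 0.3 | 3.5% | 3.4% |
| 0.4 | 7.3% | 7.2% |
| 0.5 | 12.4% | 12.3% |
| 0.7 | 27.8% | 27.7% |

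Break-even is r = 0.148 (q = 8) or 0.159 (q = 14).

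**HbA1c, allowing for pre-diabetes status as a proxy.** Suppose pre-diabetes status is baseline HbA1c dichotomised at prevalence p (an assumption). Its correlation with baseline HbA1c is k = φ(z)/sqrt(p(1 − p)), where φ is the standard normal density and z the normal cut-point. This gives 0.585, 0.700 and 0.759 at p = 0.1, 0.2 and 0.3. A raw correlation ρ then becomes partial r = ρ(1 − k²)/sqrt((1 − ρ²k²)(1 − k²)).

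| ρ | partial r at p = 0.1, 0.2, 0.3 | net narrowing (q = 8) |
|---|---|---|
| 0.3 | 0.247, 0.219, 0.201 | 2.0%, 1.3%, 0.9% |
| 0.5 | 0.424, 0.381, 0.352 | 8.4%, 6.5%, 5.4% |
| 0.7 | 0.622, 0.574, 0.538 | 20.9%, 17.2%, 14.8% |

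**Survey change scores, q = 7.** If baseline and closure variances are equal, V = (1 + r)/2, and adding the baseline score narrows the interval by 21.7%, 15.4% and 6.8% at r = 0.2, 0.4 and 0.7. With q = 13 the figures are 21.6%, 15.3% and 6.7%. If the baseline-to-closure SD ratio is c, then V = (1 − r²)/(1 + c² − 2rc), and the net narrowing is:

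| c | r = 0.2 | r = 0.4 | r = 0.7 |
|---|---|---|---|
| 0.5 | 3.3% | −0.5% | 2.7% |
| 0.7 | 10.0% | 3.9% | −1.1% |
| 1.0 | 21.7% | 15.4% | 6.8% |
| 1.3 | 33% | 28% | 23% |

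**Simulation check.** This used 3,000 trials per setting, individual allocation and no true effect. For the 6-month value (q = 8) the changes were −1.1%, 1.0% and 7.3% at r = 0, 0.2 and 0.4. For change scores (q = 7, equal variances) they were 21.9%, 15.7% and 6.8% at r = 0.2, 0.4 and 0.7. The mean arm difference stayed within 0.012 SD of zero with and without baseline, which agrees with the no-bias statement.

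**The case against.** The strongest reply is that this is a matter of efficiency in a pilot. Section III says the sample size was not chosen for power, no decision rule depends on interval width, and the comparison is unbiased either way. The size of the gain rests on an assumed correlation. Baseline is taken in the first or early second trimester and the outcome 6 months after delivery, with the DPP sessions in between for two arms, so r may be modest. For MAP the documents offer no anchor for r at all. All of this stands. It limits the finding to a recommended improvement and is why the gain is shown as a range.

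The number of completers can also be disputed. Section III says 60 will be recruited, and 20% attrition from 60 leaves 48. At N = 48 the cost at r = 0 rises to 1.5% (q = 8) or 1.8% (q = 14), and break-even to r of about 0.17 or 0.19. That is a small shift. Attrition of that size would also bring in the plan's multiple imputation, which these complete-case formulas do not model.

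The change-score gains depend on the SD ratio, and under some ratios they disappear. This is correct and is shown above, but it concerns the secondary survey models.

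Finally, the HbA1c sentence gives no time point, so a change from baseline could be meant. The recommendation is sound on that reading too: adding the baseline value gives the same adjusted arm comparison whether the outcome is the 6-month value or the change.

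**Conclusion.** The concern holds. Both Aim 2 models omit the baseline value of a primary outcome that is measured at baseline. The consequence is wider intervals and uncorrected chance imbalance; there is no bias, provided allocation is individual. With 60 completers, the intervals forgo about 1% to 7% of narrowing at partial r of 0.2 to 0.4. A gain of 28% would need r = 0.7. If pre-diabetes status already captures part of baseline HbA1c, raw correlations of 0.3 to 0.5 give a gain of about 1% to 8% for that outcome. The downside of adjusting is about 1%, or up to 1.8% with 48 completers. All these gains rest on assumed correlations. The plan should be changed, but the point does not undermine the trial.

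**What to change.** In Section III, Aim 2:

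- State that the outcome is the 6-month value for both HbA1c and MAP.
- Add continuous baseline HbA1c to the HbA1c model and baseline MAP to the MAP model, alongside the eight covariates.

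In the survey comparisons, add the baseline score to each of the six change-score models.

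The cost is SAP wording and one degree of freedom per model, with no new data. Making the change before analysis also removes any later discretion over whether to adjust for baseline.

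Two minor wording points can be settled in the same edit; neither bears on the finding. Section I.A and the Aim 2 text list HbA1c at delivery but Table 5 does not, so they should be reconciled. The brackets in the Aim 2 formula for MAP should be checked, although the misplacement may come from text extraction.

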Aim 3: Test the efficacy of Tx1 to increase any breastfeeding through 6 months postpartum among women with a BMI  $\geq$  25. The outcome of interest is breastfeeding through 6 months postpartum; it will be measured at delivery, and at weeks 1, 3, and 6 postpartum and at 3 months (13 weeks) and 6 months (26 weeks) postpartum. The risk of stopping "6 month postpartum breastfeeding" in Tx1 relative to Tx2 and Tx3 will be estimated using Zou's modified Poisson regression approach. The outcome in Zou's modified Poisson regression is binary, and it does not take into account the time until which any breastfeeding was done before stopping. However, it provides an interpretation-friendly estimate of the probability of stopping "6 month postpartum breastfeeding." Additionally, the Cox Ph model will be used to compare the risk (hazard) of stopping breastfeeding across each study arm. Unlike Zou's modified Poisson approach, the Cox model takes into account the time of breastfeeding. Any participants who are lost to follow-up will be treated as censored events and participants who stop

breastfeeding during the follow-up are the events of interest. In addition, participants who performed any breastfeeding until 6 months will be treated as administratively censored events. The model will be adjusted for the same covariates listed above under Aims #1 and #2.

Missing data. Owing to the design of the study and non-transient nature of the study population, we anticipate few to none missing observations. Any missing observation that can be attributed to either attrition or nonresponse will be considered missing at random. Depending on the proportion of missingness, complete case analysis (less than 5% missing) or the multiple imputation method will be used to impute missing data. For longitudinal response (postpartum weight measurements), the last observation will be carried forward to impute the missing response. Results based on imputed data will be compared to findings from complete case analysis, to assess the effect of missingness on study findings.

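### Aim 1 carries the last postpartum weight forward, which records zero loss after dropout and conflicts with the plan's own missing-at-random assumption

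*Combined protocol and SAP*

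**What the plan says.** The Missing data paragraph of Section III makes these statements:

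- Expected amount: "we anticipate few to none missing observations".
- Mechanism: "Any missing observation that can be attributed to either attrition or nonresponse will be considered missing at random".
- General method, depending on how much is missing: "complete case analysis (less than 5% missing) or the multiple imputation method will be used to impute missing data".
- Exception for the Aim 1 outcome: "For longitudinal response (postpartum weight measurements), the last observation will be carried forward to impute the missing response".
- Check: "Results based on imputed data will be compared to findings from complete case analysis".

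The Aim 1 paragraph defines the outcome: "The difference in postpartum weight (weight loss) between two consecutive time points will be computed". "Weight will be measured at delivery, and at weeks 1, 3, and 6 postpartum", then at 13 and 26 weeks, so six weights give five interval losses. These go into a generalized estimating equation (GEE) model whose working correlation is to be chosen after the data are assessed. The analysis is to follow intention-to-treat.

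Section II.D expects dropout: "Given an attrition rate of 20%, this will leave us with 60 women total". Section II.F & G and Table 2 place the postnatal half of the Diabetes Prevention Program (Phase II) in weeks 6 to 20 postpartum, for Tx1 and Tx2 only.

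**The concern.** The paragraph adopts MAR and names a method that fits it, then uses a different method for the one outcome measured repeatedly. Carrying a weight forward assumes that a woman's weight stays fixed from her last visit. MAR says something else: given what was observed, her later weights resemble those of comparable women who stayed. Because the outcome is a set of consecutive differences, the conflict is exact, and every later interval is entered as zero loss.

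Phase II begins at week 6, so a woman last weighed at or before week 6 contributes none of its effect. The Tx1 and Tx2 comparisons with usual care are most exposed. At stake are the Aim 1 estimates and their confidence intervals. The Sample Size paragraph says the results will help size the next trial but not which quantity will be used, so that harm arises only if the weight-loss estimate is one of them.

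**Working it through.** **1. The plan's attrition figure.** 72 × 0.80 = 57.6, not 60. Retaining 60 of 72 means losing 12/72 = 16.7%. Both 16.7% and 20% are used below. Neither is compatible with expecting almost no missing data.

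**2. What carrying forward does.** If the last weight is at visit k, all later weights equal it and all later differences are 0. With filled data, the unadjusted GEE arm effect equals one fifth of the arm difference in total loss, under independence or exchangeable correlation (confirmed by fitting both). The kg figures below refer to total loss from delivery to week 26. Divide them by five for the per-interval coefficient; percentages are unchanged. A missed visit followed by a return leaves a woman's total unchanged, but it can still move the GEE estimate if the working correlation weights intervals unequally.

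**3. Assumptions, none from the documents.** Cumulative loss is 5, 7, 8, 9 and 10 kg at weeks 1, 3, 6, 13 and 26. The last visit of a woman who drops out is equally likely to be delivery or week 1, 3, 6 or 13. The true arm difference is 2.5 kg, either proportional to loss or arising after week 6 (1.0 kg by week 13, 2.5 kg by week 26).

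- Loss captured: (0 + 5 + 7 + 8 + 9)/5 = 5.8 of 10 kg, a shortfall of 4.2 kg (0.42).
- Late effect captured: (0 + 0 + 0 + 0 + 1.0)/5 = 0.2 of 2.5 kg, a shortfall of 0.92.

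**4. Equal dropout.** Shrinkage = dropout after delivery × shortfall. If half of attrition precedes delivery, dropout among women with a delivery weight is 8.33/91.67 = 9.1% or 10/90 = 11.1%.

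| Dropout after delivery | Late effect | 2.5 kg reads | Proportional effect |
|---|---|---|---|
| 16.7% | 15.3% | 2.12 kg | 7.0% |
| 20% | 18.4% | 2.04 kg | 8.4% |
| 9.1% | 8.4% | 2.29 kg | 3.8% |
| 11.1% | 10.2% | 2.24 kg | 4.7% |

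**5. Unequal dropout, no true effect.** False difference = 4.2 kg × difference in dropout, against the arm that loses more women.

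- 25% vs 15%: 4.2 × 0.10 = 0.42 kg. 30% vs 10%: 4.2 × 0.20 = 0.84 kg.
- With half before delivery: 4.2 × (14.3% − 8.1%) = 0.26 kg and 4.2 × (17.6% − 5.3%) = 0.52 kg.

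**6. Does the planned check expose it?** Simulation with 20 women per arm, about 20% dropout after delivery in each arm and a late effect of 2.5 kg. Dropout depends on earlier loss in usual care only; the slope is the rise in log-odds per kg less lost.

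| Slope | Carried forward | Complete case | Likelihood under MAR |
|---|---|---|---|
| 0 | 2.07 | 2.51 | 2.47 to 2.52 |
| 0.3 | 1.84 | 2.00 | 2.47 to 2.52 |
| 0.6 | 1.72 | 1.66 | 2.47 to 2.52 |

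The check shows a gap in the first row. In the third, both estimates are low and close together, so agreement would falsely reassure. The MAR result is near 2.5 because the data were generated as MAR. Standard errors were about 1.2 to 1.4 kg.

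**7. A second set of assumptions.** 24 women per arm, a true effect of 3.0 kg arising after week 6, and dropout after week 6 more likely with less loss. The rates are those at average week-6 loss; overall dropout is higher (10%, 20% and 30% become about 18%, 28% and 36%).

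| Program / usual care | Carried forward | Complete case | Imputation under MAR |
|---|---|---|---|
| 20% / 20% | 2.13 | 3.00 | 2.99 |
| 10% / 30% | 2.78 | 2.28 | 2.99 |
| 30% / 10% | 1.59 | 3.71 | 3.00 |

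With no true effect, the two unequal rows gave +0.35 and −0.33 kg carried forward, −0.72 and +0.72 kg complete case, and about 0 under MAR. Rejection after carrying forward stayed at 5% to 6%.

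**The case against.** The strongest reply concerns the target. Suppose leaving the study ends the program and any further benefit. At 20% dropout the average effect is then 0.8 × 2.5 + 0.2 × 0.2 = 2.04 kg, exactly the carried-forward figure, and the MAR value is too high. This has force: the size of the equal-dropout shrinkage depends on measuring against MAR. But MAR is the plan's own stated assumption, and the agreement holds only when dropout is equal. Ordinary postpartum loss continues after a woman leaves, so the false difference in step 5 remains.

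A second reply is that the effect is small for a pilot not powered for efficacy. That stands as to size. A reader might infer inflated false-positive rates or a bias in a fixed direction; neither is supported. Rejection stayed near 5%, and with unequal dropout the error can go either way.

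A reader might also infer that starting the outcome at delivery, after the prenatal sessions in Tx1 and Tx2, is an error, or that the Tx3 contrasts then describe the postnatal phase only. The documents do not support this. Hypothesis 1 is worded as postpartum loss. Habits formed in pregnancy can carry into postpartum loss, and lower gestational gain can reduce the loss that follows. What is true is narrower: a weight difference already present at delivery is not credited in the Tx3 contrasts.

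**Conclusion.** The point holds and should be fixed. The inconsistency between carrying weights forward and the stated MAR assumption is textual and certain. The complete-case comparison does not repair it: complete case is itself biased under MAR when dropout depends on earlier loss in one arm, and the plan does not say which result governs.

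The size is uncertain and modest. At the plan's attrition figures, the step 3 assumptions give roughly 4% to 18% shrinkage with equal dropout and about 0.3 to 0.8 kg of false difference with a gap of 10 to 20 points. The higher overall dropout in step 7 gives more shrinkage. All of this rests on assumed trajectories and dropout timing, and the biases in the scenarios of steps 4 to 6 are below one standard error at 20 per arm.

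**What to change.** 1. Make the multiple imputation already named in the Missing data paragraph the primary method for postpartum weights. Impute the weights by arm from baseline, delivery and earlier postpartum weights and the planned covariates, then compute the differences and fit the planned GEE. A likelihood-based repeated-measures model is an acceptable alternative but not required.
2. Say how women lost before delivery are handled. They have no postpartum weight to carry forward and the plan is silent on them; intention-to-treat calls for including them in the imputation.
3. Keep carrying forward and complete case as sensitivity analyses, and state that the MAR result is primary.
4. Reconcile the attrition statements in Section II.D and the Missing data paragraph.

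Optional, and not a correction: report 26-week weight adjusted for baseline weight as a secondary description, which would credit any difference already present at delivery.

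Cost: no new data, since Table 5 already collects the weights. There is a little more analysis work. With 24 women randomized per arm the imputation model must be kept small, so a reduced covariate set should be named in advance as a fallback. The protocol text changes, so Section IV.I requires IRB approval first.
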